## 2. Background and Rationale

Patellofemoral pain (PFP) is the most common running-related overuse injury, with prevalence up to 17% among runners. Increased patellofemoral joint stress (PFJS) is a major biomechanical contributor to PFP. Traditional strengthening exercises improve function but do not alter running biomechanics. Gait retraining, particularly cadence modification, has been proposed as a promising approach to reduce PFJS and alleviate symptoms. However, evidence from randomized controlled trials remains limited. This study investigates whether wearable device-assisted gait retraining reduces pain, improves function, and modifies running biomechanics in female runners with PFP compared to education alone.

## 3. Objectives

Primary Objective: To determine the effectiveness of wearable device-assisted gait retraining on pain reduction during running in female runners with PFP.

Secondary Objectives:

- To assess improvements in function (Anterior Knee Pain Scale, AKPS)
- To examine changes in running mechanics (knee kinematics, kinetics, PFJS)
- To evaluate adherence, feasibility, and safety of wearable device-assisted gait retraining

## 4. Study Design

Type: Randomized, controlled, single-blind, parallel-group trial

Allocation: 1:1 randomization

Masking: Outcome assessors blinded; participants not blinded due to intervention nature

Arms:

- Intervention Arm: Education + Wearable device-assisted gait retraining
- Control Arm: Education only

Study Duration: 18 weeks per participant (6-week intervention + 12-week follow-up)

## 5. Participants

Inclusion Criteria:

- Female, age 18–45 years
- Unilateral/bilateral anterior knee pain > 4 weeks
- VAS pain  $\geq 3/10$  during running and  $\geq 2$  of the following: jumping, squatting, kneeling, stairs, prolonged sitting, or resisted knee extension
- Running  $\geq 15$  km per week
- Natural rearfoot striker (verified by high-speed video)

Exclusion Criteria:

- Acute trauma, history of patellar dislocation, meniscal/chondral lesions
- Prior knee surgery or injection in past 12 months
- Rheumatologic, neurologic, or degenerative disease

- Pregnancy

## 6. Interventions

### 6.1 Control Group (Education)

Delivered via WeChat platform. Content: PFP education, load management strategies, symptom-based training modifications, and strengthening exercises (quadriceps & hip). Self-monitored running program guided by pain thresholds.

### 6.2 Intervention Group (Gait Retraining + Education)

Same education program as control. Gait retraining protocol: 6-week program, twice per week. Step rate increased by 10%, monitored via smartwatch (Huawei GT4). Real-time cadence feedback via auditory metronome cues. Feedback frequency: every session (weeks 1–4), once (week 5), faded (week 6). Duration progressed from 15 min to 30 min per session. Pain monitoring: ≤ 3/10 during running, return to baseline within 60 min.

## 7. Outcomes

### 7.1 Primary Outcome

Pain during running (VAS-R, 0–100 mm) at baseline, 6 weeks, and 18 weeks

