## **9. Randomization and Blinding**

Random sequence generated by independent statistician. Allocation concealed in sequential opaque envelopes. Assessors blinded to group assignment. Participants instructed not to disclose intervention to evaluators.

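### Is the primary outcome too loosely defined, given that the training programme itself limits pain during running?

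*Combined protocol and SAP*

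**What the plan says.** Section 7.1 gives the whole definition of VAS-R: "Pain during running (VAS-R, 0–100 mm) at baseline, 6 weeks, and 18 weeks". Section 7.2 lists usual and worst pain as separate scales, also without a recall period.

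Three other places bear on it:

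- **Entry (Section 5).** Participants need "VAS pain $\geq 3/10$ during running", and the knee criterion is "Unilateral/bilateral anterior knee pain > 4 weeks". No rule says which knee is rated when both hurt.
- **Training rules (Section 6).** Control participants follow a "Self-monitored running program guided by pain thresholds", with no number given. The intervention arm receives the "Same education program as control" and, within the retraining protocol, "Pain monitoring: ≤ 3/10 during running, return to baseline within 60 min".
- **Masking (Sections 4 and 9).** Section 4 has "participants not blinded due to intervention nature"; Section 9 has "Assessors blinded to group assignment".

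Section 8 plans for a 20 mm difference with 22 participants per group. Section 10 adjusts for baseline and uses multiple imputation.

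**The concern.** The quantity measured as the primary outcome shares its name with a quantity that the programme restrains. Everyone enters at 3/10 or above, and the retraining rule is 3/10 or below, so the rule meets the lowest entry value exactly. A participant who keeps to it must either improve or run more gently. A low rating could then mean a better knee or an easier run.

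Participants know their arm and rate themselves. If the run is left open they might also influence what is rated, and blinding the assessor would not prevent that. With a numbered rule in one arm's text and an unnumbered one in the other's, it is natural to ask whether the restraint is equal. At stake is the meaning of the primary result: pain on a comparable run, or pain on runs that a rule holds down. The randomised comparison of the two packages stays valid either way.

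**Working it through.** **Inputs.** Scale 0–100 mm (7.1); training rule 3/10 (6.2); entry minimum 3/10 (5); target 20 mm, 80% power, alpha 0.05, 15% dropout, 22 per group (8). Assumption: the 0–10 scale converts linearly, so 3/10 × 100 mm = 30 mm.

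**The plan's own figure.** Section 8 states no SD, so 22 per group cannot be reproduced directly. Solving backwards for a two-sided, two-sample t-test, an SD of 20.5 mm needs 18 per group, and 18 / (1 − 0.15) = 21.2, rounded up to 22. SDs of about 20.2 to 20.8 mm all give 22.

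**What range could VAS-R take?** This depends on whether rated runs fall under the rule and the rule is kept.

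| Rated runs | Range of VAS-R | What 20 mm means |
|---|---|---|
| Outside any limit, both arms | 0–100 mm | 20/100 = 20% of the range |
| Limited in both arms | 0–30 mm | 20/30 = 67%; intervention mean at most 30 − 20 = 10 mm, control mean at least 0 + 20 = 20 mm |
| Limited in the intervention arm only | at most 30 mm there | control mean of 30 + 20 = 50 mm or more gives at least 20 mm |

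*First row.* There is no effect on the comparison.

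*Second row.* A share of the range is not power. A score confined to 0–30 mm has an SD of at most 30/2 = 15 mm, and at SD 15 mm the t-test needs 10 per group, or 10/0.85 = 11.8, so 12 after dropout. The attainable difference would shrink as well, and the net result is unknown. The back-solved SD of 20.2 to 20.8 mm exceeds 15 mm, which suggests that the sample size was planned for an outcome not confined to 30 mm. This is an inference from an unstated SD and an assumed t-test.

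*Third row.* The arithmetic bounds the gap; it does not attribute it. If retraining brought every intervention participant to 30 mm or below, the same control mean of 50 mm would give the same 20 mm or more, and the rule would have contributed nothing. The gap belongs to the rule only if unrestricted pain in the two arms would have been equal. A simulation that assumes this, together with an SD of 21 mm, ratings clipped to 0–100 mm, full compliance and a limit in one arm only, gives differences of 8.4, 14.3 and 21.9 mm for unrestricted means of 30, 40 and 50 mm. None of those assumptions comes from the documents.

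**Which row do the sections support?** Read in order, Section 6.2 gives the retraining programme, its length and weekly frequency, the cadence feedback, the minutes per session, and then the pain rule. The natural scope is the retraining sessions in weeks 1 to 6. Section 7.1 does not refer back to it, and no section extends it to week 18. Sections 6.1 and 6.2 together give both arms the same education, which includes symptom-based changes to training. A limit on rated runs in one arm only is therefore the least supported reading.

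**The case for a change.** The strongest case for a change is that this is the primary outcome, that adding the missing words would cost little, and that a reader cannot replicate a measurement whose run, recall period and knee are unstated. Participants are unblinded, the control threshold has no number, and the retraining rule starts exactly where eligibility starts, so in this trial the silence matters more than in most pain trials.

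Part of that stands. The details are absent, bilateral pain is admitted without an index knee, and the documents do not say whether any training threshold applies when VAS-R is rated. The scope of the rules in 6.1 and 6.2 is for the investigators to state; none is suggested here.

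The rest does not carry. Silence about the run does not show that participants choose it. Section 7.2 includes motion and ground-reaction measurements, so some assessed run exists, although its link to VAS-R is not stated. Weekly mileage is also collected and would show if one arm ran much less.

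Nor is there a clearly better text to insert. A standard run makes ratings alike but may represent ordinary running less well, may add a procedure at three visits, and needs a rule for shortened runs that Section 10 lacks. A recall rating stays closer to daily running, but leaves the influence of training rules open and turns people who stop running into missing values. That is a fair trade-off between two defensible procedures.

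**Conclusion.** No change to the plan follows. Section 7.1 omits operational detail, but the documents neither contradict themselves nor show a bias. The effect on the between-arm difference is zero if rated runs fall outside the training rule, and its size and direction cannot be estimated otherwise, because baseline pain, compliance and the scope of the rule are not given. The 30 mm ceiling holds only if the rule is kept on the rated runs. A pain-monitoring rule does not cap the scale: someone may exceed it before changing the run, and rate that pain.

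The conclusion rests on two assumptions: that the 6.2 rule governs retraining sessions, its natural reading, and that VAS-R is collected in the same way in both arms at each visit, as any sensible conduct of a blinded-assessor trial would have it. The investigators have to fix a run or recall period and a knee in order to collect the score at all, and the trial report is the natural place to describe what was used. If rated runs proved to be limited in one arm only, the result would need more careful interpretation, but nothing in the documents points that way.

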### 7.2 Secondary Outcomes

- VAS-U (usual pain), VAS-W (worst pain)
- Function: Anterior Knee Pain Scale (AKPS)
- Running-related measures: weekly mileage, cadence (smartwatch logs)
- Running mechanics: 3D kinematics, GRF, PFJS and contact force calculations

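### Does the smartwatch cadence outcome need a control-arm source and a rule separating cued from uncued runs?

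*Combined protocol and SAP*

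**What the plan says.** Section 7.2 (Secondary Outcomes) includes the line "Running-related measures: weekly mileage, cadence (smartwatch logs". It does not restrict cadence to one arm, give visits for it, or say which runs count.

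The watch is described in Section 6.2, as part of the retraining program: "Step rate increased by 10%, monitored via smartwatch (Huawei GT4). Real-time cadence feedback via auditory metronome cues". That section also sets the cueing schedule, "Feedback frequency: every session (weeks 1–4), once (week 5), faded (week 6", and the session length, "Duration progressed from 15 min to 30 min per session". There are two sessions a week for six weeks.

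For the other arm, Section 4 has "Control Arm: Education only", and Section 6.1 describes education by WeChat with a "Self-monitored running program guided by pain thresholds". Neither mentions a watch or a cadence log, and neither rules one out.

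Two other places bear on what the logs are for. One of the secondary objectives in Section 3 is "To evaluate adherence, feasibility, and safety of wearable device-assisted gait retraining". Section 2 says that "Gait retraining, particularly cadence modification, has been proposed as a promising approach to reduce PFJS and alleviate symptoms". Section 10 gives general methods and says nothing specific to cadence.

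**The concern.** Read literally, Section 7.2 puts cadence beside usual pain, worst pain, AKPS and running mechanics, all of which one would expect to be compared between arms. Two difficulties would then arise.

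- **Control source.** Repeated measures ANOVA, or regression adjusted for baseline, needs values from both arms. If controls have no logs, multiple imputation cannot credibly supply an outcome that is missing for a whole arm. If their values come from another device, the arms are measured differently.
- **Cued running.** A log recorded while the runner follows a metronome set above her usual step rate shows whether she kept to the beat. It does not show whether her unprompted gait changed. An average over all logged runs mixes the two.

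At stake is the reading of one secondary measure. A reader could take a cadence rise in the intervention arm as evidence of retained gait change, which the background section makes an interesting question, when part of it was compliance with the cue.

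**Working it through.** The plan gives no expected cadence difference to reproduce; the sample size in Section 8 concerns VAS only. The check has two parts: what the documents support, and how large the artefact could be.

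**1. Which reading the documents support**

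| Place | Bearing on cadence |
|---|---|
| Section 3, mechanics objective | Names knee motion, kinetics and patellofemoral stress; cadence is not among them |
| Section 3, adherence objective | Needs a measure; the running logs are the only listed item that could plausibly serve |
| Section 6.2 | The watch is the means of monitoring the step-rate target |
| Section 7.2 | Listed as an outcome, with no arm or visit given |
| Section 10 | No cadence analysis specified |

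The first three rows point to adherence data, for which cued sessions are the right ones to log and no control value is needed. The fourth leaves the matter open. No row specifies a between-arm comparison of pooled cued logs.

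**2. Size, if such a comparison were made**

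*Inputs from the documents:* 6 × 2 = 12 sessions, 15 to 30 min each, a 10% step-rate increase, and an entry minimum of 15 km/week (Section 5).

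*Assumptions:* weekly session lengths of 15, 18, 21, 24, 27 and 30 min; speed 8–12 km/h, equal in cued and uncued runs; the full 10% reached when cued; retraining counted within weekly distance; 30 km/week as a second case; one of two sessions cued in week 5; in week 6, from none up to half of the session time cued.

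*Sessions with any cueing:* 8 + 1 + (0 to 2) = 9 to 11 of 12, or 75% to 92%.

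*Formula:* let s be the cued share of weekly distance and u the true percentage gain in uncued running. The pooled gain is 10s + u(1 − s), so the artefact (pooled gain minus u) is s(10 − u). It is largest at u = 0 and vanishes at u = 10.

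*Results at u = 0:*

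| Period | Cued time per week | Cued distance | Artefact at 15 km/week | Artefact at 30 km/week |
|---|---|---|---|---|
| Weeks 1–4 | 2 × 19.5 min = 0.65 h | 5.2–7.8 km | 3.5%–5.2% | 1.7%–2.6% |
| Week 5 | 27 min = 0.45 h | 3.6–5.4 km | 2.4%–3.6% | 1.2%–1.8% |
| Week 6, none cued | 0 | 0 | 0 | 0 |
| Week 6, half of 1.0 h cued | 0.5 h | 4–6 km | 2.7%–4.0% | 1.3%–2.0% |
| Week 18 | none described | 0 | 0 | 0 |

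Example: 5.2/15 = 34.7%, and 34.7% × 10% = 3.5%.

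With u = 5 the weeks 1–4 range at 15 km/week halves: 0.347 × 5 = 1.7% to 0.520 × 5 = 2.6%.

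*Weighting by run instead of distance, u = 0:*

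- The 12 sessions alone: 9/12 to 11/12 of 10% = 7.5% to 9.2%.
- One further uncued run a week: 9/18 to 11/18, giving 5.0% to 6.1%.
- Two further uncued runs a week: 9/24 to 11/24, giving 3.8% to 4.6%.

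The spread across these cases shows how far the size depends on assumptions that the documents do not settle.

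**The case for a change.** The strongest case for a change is that a listed outcome should be defined by arm, time and measurement condition, and this one is not. If controls also wear the watch, one sentence would settle the first difficulty, but the cued-run problem would remain. If the item is adherence data, it could have been labelled so. With up to about half of the 10% target able to appear in weeks 1–4 without any change in uncued running, the result can turn on an unstated rule.

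The textual part stands: the wording is incomplete, and the adherence reading is well supported but not certain. The rest carries less weight.

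- The largest figures fall in weeks 1–5. The only assessment times the plan gives are baseline, 6 weeks and 18 weeks, for running pain in Section 7.1. At week 6 the range starts at nil, and at week 18 no artefact is expected.
- Zero carry-over is the extreme case: it supposes that retraining does nothing outside cued time.
- Missing visits are common to every item in Section 7.2 and are not a fault of the cadence item in particular.
- If controls have no logs, the comparison cannot be run at all. That would be obvious to the analyst and would not bias a result unnoticed.
- The concrete replacement, step rate from the mechanics sessions at a fixed individual speed, gives up habitual cadence for laboratory cadence and relies on mechanics visits whose timing the plan does not state. It trades one limitation for another.

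**Conclusion.** No change to the plan is needed. This is missing detail on one secondary measure, of a kind that analysts fill sensibly. Logs from cued sessions serve the adherence objective as they stand. Anyone who wished to compare arms would see from the Section 6.2 schedule which weeks contain cueing, and would need like-for-like uncued running in both arms.

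On the assumptions above, the artefact at the entry minimum is at most 5.2% on a distance basis in weeks 1–4, between nil and 4.0% in week 6, and absent at week 18. Run-based weighting gives larger illustrative values, up to 9.2% when the log holds retraining sessions only. Every figure assumes that none of the gain carries over, and each falls to zero if uncued running fully retains it. All are also conditional on a between-arm analysis that the plan does not specify. No stated figure changes, and the VAS-R comparison does not depend on the logs.

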### 7.3 Safety Outcomes

Adverse events (pain exacerbation, injuries, withdrawal)

## **8. Sample Size**

Sample size estimated with G\*Power. Detectable difference: 20 mm VAS (MCID for PFP).

Power: 80%,  $\alpha = 0.05$ . Estimated: 22 participants per group (total n=44), accounting for 15% dropout.

## **9. Randomization and Blinding**

Random sequence generated by independent statistician. Allocation concealed in sequential opaque envelopes. Assessors blinded to group assignment. Participants instructed not to disclose intervention to evaluators.

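### Assessor blinding is claimed for every outcome but not secured for running mechanics, because the step-rate change given to one arm is visible in the gait data themselves

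*Combined protocol and SAP*

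**What the plan says.** Section 4 (Study Design) sets the masking by role: "Masking: Outcome assessors blinded; participants not blinded due to intervention nature". Section 9 (Randomization and Blinding) repeats the claim and adds one measure: "Assessors blinded to group assignment. Participants instructed not to disclose intervention to evaluators". Neither section limits the claim to particular outcomes.

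Section 6.2 gives the intervention arm a cadence target: "Step rate increased by 10%, monitored via smartwatch (Huawei GT4". Section 6.1 gives the control arm none: "Content: PFP education, load management strategies, symptom-based training modifications, and strengthening exercises (quadriceps & hip".

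Section 7.2 lists as secondary outcomes both "Running-related measures: weekly mileage, cadence (smartwatch logs" and "Running mechanics: 3D kinematics, GRF, PFJS and contact force calculations". Section 3 makes change in running mechanics a secondary objective. The primary outcome in Section 7.1 is "Pain during running (VAS-R, 0–100 mm) at baseline, 6 weeks, and 18 weeks".

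The documents do not say who the assessors are, or whether the same person collects the pain and function scores and runs the gait test. They also do not say who reads the watch logs, whether gait files are coded before processing, or whether cadence is free or controlled during the laboratory run.

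**The concern.** A participant's silence protects an assessor only if the data carry no information about the arm. Here the treatment contrast is itself measured. A runner trained to a higher step rate shows it in the motion and force recordings and in the watch log, and a handler who also has the baseline file can compare the two.

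Two groups of outcomes could be affected, in different ways:

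- **Running mechanics.** Kinematics, joint stress and contact force are calculated from recordings. Such processing can involve operator choices (marker labelling, event detection, stride selection, filtering), and the plan fixes no rules for them. An operator who can tell the arm has room, even unintentionally, to favour retraining.
- **Pain and function scores (VAS-R, VAS-U, VAS-W, AKPS).** If an evaluator administers these after watching the run or reading the logs, that evaluator's blinding may already be lost. This is conditional on a procedure the documents do not describe.

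In both cases the results would be reported under a single-blind label that the described safeguard does not support.

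**Working it through.** The plan gives no figure for blinding, so there is nothing to reproduce. The check asks how well a data handler could guess the arm.

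**Inputs**

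- Shift in step rate: 10% in the intervention arm (Section 6.2) and 0% in controls. The zero is an assumption, since Section 6.1 sets no cadence target.
- Half uptake or half retention: 5% (assumption).
- Allocation 1:1 (Section 4), so guessing without information is right 50% of the time.
- SD of a runner's change from baseline: 3% to 5% (assumption).
- SD between runners when the baseline is not available: 6% (assumption).
- Cadence in the laboratory is self-selected (assumption).

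The documents give no cadence SD.

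**Formula.** With two equally likely groups, a common SD and a cut-off at the midpoint, P(correct) = Φ(half the shift / SD).

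| What the handler sees | Shift | SD | Calculation | P(correct) |
|---|---|---|---|---|
| Change from baseline | 10% | 3% | Φ(5/3) | 95% |
| Change from baseline | 10% | 5% | Φ(5/5) | 84% |
| Change from baseline | 5% | 3% | Φ(2.5/3) | 80% |
| Change from baseline | 5% | 5% | Φ(2.5/5) | 69% |
| Participant and visit masked | 10% | 6% | Φ(5/6) | 80% |
| Participant and visit masked | 5% | 6% | Φ(2.5/6) | 66% |

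**Sensitivity to the assumed SDs**

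- A 2% SD of change gives Φ(5/2) = 99% at full uptake and Φ(2.5/2) = 89% at half uptake.
- For one follow-up recording with no baseline, work in steps per minute. With mean cadence 160 and SD 12, the shift is 16 and Φ(8/12) = 75%. With mean 170 and SD 6, the shift is 17 and Φ(8.5/6) = 92%.

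Every case lies above 50% and none reaches certainty. Masking participant and visit lowers the figure but does not restore blinding: at full uptake it moves from 84–95% to 80%, and at half uptake from 69–80% to 66%.

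**One further route is open.** Section 6.2 names the watch only for the intervention arm and Section 6.1 mentions no device, while Section 7.2 lists "cadence (smartwatch logs" as an outcome without naming an arm. If controls wear no watch, the existence of a log reveals the arm. The documents do not settle whether they do.

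**The case against.** A reader might infer that assessor blinding cannot hold at all in this trial. The documents do not support that. They do not say that whoever collects the scores sees the run or the logs, and separate staff or coded files would be consistent with the text. The non-disclosure instruction is the only measure described, but it is not stated to be the whole scheme. Inference is also probabilistic, and weaker if the cadence change is partial or fades. These objections stand, and they limit the point to blinding that is not secured.

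A reader might also infer that the primary outcome is compromised by this route. That is not shown either. Nothing says that VAS-R or AKPS is collected by interview. The larger exposure for these scores is that participants know their arm, which Section 4 discloses and which perfect assessor masking would leave unchanged.

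Three more objections carry weight:

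- Smartwatch cadence is recorded by a device, so an unmasked reader has little room to alter it.
- The probabilities measure guessing, not bias, and they presume that someone actually makes the comparison. If gait processing is fixed or automated, little bias can enter.
- When cadence is the treatment, gait data will carry information about the arm, so any remedy is partial.

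What survives is that Sections 4 and 9 assert blinding without limit, the described safeguard does not address information carried by the data, and no processing rules are fixed for a set of outcomes that serves a stated objective.

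**Conclusion.** The concern holds in limited form. Blinding is not secured for the mechanics outcomes: a person handling the gait recordings can infer allocation with probability of roughly 66% to 95%, given assumed SDs of 3% to 6%, no cadence change in controls, self-selected laboratory cadence, and uptake between half and full. The size of any resulting bias cannot be derived from the documents.

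For VAS and AKPS, loss of assessor blinding is possible but unsettled, and it is secondary to the open-label knowledge of the participants. Smartwatch cadence is little affected. This is worth correcting because the blinding claim is broader than the procedure behind it and the correction is cheap. It does not undermine the trial as a whole.

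**What to change.** 1. Have participants complete VAS-R, VAS-U, VAS-W and AKPS themselves before any evaluator sees the running test or the watch logs. If VAS-R refers to the test run, the participant records it directly and the evaluator does not read it.
2. Check each gait trial promptly for usability. Then have someone who does not process the data, such as the independent statistician already named in Section 9, code the motion and force files to remove participant and visit. Process the files in random order, with event-detection, stride-selection and filter rules locked beforehand. Because coding alone leaves the arm partly guessable, the locked rules are an essential part of this step.
3. In Sections 4 and 9, limit the blinding claim to these steps. State that people handling gait data may still infer allocation, and that assessor blinding does not protect participant-reported outcomes.

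The cost is the file-coding work, a set order of events at visits, later processing of gait data, and a few lines of protocol text. The prompt usability check guards against finding unusable trials too late. Sample size, power and alpha do not change.
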